16. APPENDIX

Table 1. Diagnosis Codes for Identifying HIV infection

Code	Type	Description
042	ICD-9-CM	HIV-1 infection
V08	ICD-9-CM	Asymptomatic HIV disease
B20	ICD-10-CM	HIV-1 infection
Z21	ICD-10-CM	Asymptomatic HIV disease

Table 2. National Drug Codes for Identifying HIV Antiretrovirals (see excel)

Table 3. National Drug Codes and CPT® Codes for Identifying PCV13 Vaccination

Code	Type	Description
50090194409	NDC	13-valent pneumococcal conjugate vaccine
54569661300	NDC	13-valent pneumococcal conjugate vaccine

PFIZER CONFIDENTIAL

CT24-WI-GL02-RF02 5.0 Non-Interventional Study Protocol Template For Secondary Data Collection Study

01-Aug-2023

Page 29 of 46

50090194400	NDC	13-valent pneumococcal conjugate vaccine
00005197105	NDC	13-valent pneumococcal conjugate vaccine
00005197104	NDC	13-valent pneumococcal conjugate vaccine
00005197102	NDC	13-valent pneumococcal conjugate vaccine
00005197101	NDC	13-valent pneumococcal conjugate vaccine
90670	CPT	13-valent pneumococcal conjugate vaccine

Table 5. Diagnosis Codes for Identifying Pneumococcal Pneumonia and Pneumonia with Unspecified Causes

Condition	ICD-9-CM		ICD-10-CM	
	Codes	Description	Codes	Description
Pneumococcal pneumonia	481	Pneumococcal pneumonia	J13	Pneumonia due to Streptococcus pneumoniae
	482.9 + 041.2	Bacterial pneumonia, unspecified + pneumococcus	J15.9 + B95.3	Unspecified bacterial pneumonia + Streptococcus pneumoniae
	485 + 041.2	Bronchopneumonia, organism unspecified + pneumococcus	J18.0 + B95.3	Bronchopneumonia, unspecified organism + Streptococcus pneumoniae
	486 + 041.2	Pneumonia, organism unspecified + pneumococcus	J18.8 + B95.3 J18.9 + B95.3	Other pneumonia, unspecified organism + Streptococcus pneumoniae Pneumonia, unspecified organism + Streptococcus pneumoniae
	510.x + 041.2			Empyema + pneumococcus
	510 + 041.2	Empyema with fistula + pneumococcus	J86.0 + B95.3	Pyothorax with fistula + Streptococcus pneumoniae
	510.9 + 041.2	Empyema without mention of fistula + pneumococcus	J86.9 + B95.3	Pyothorax without fistula + Streptococcus pneumoniae
Pneumonia with unspecified causes	480-486 487.0			Viral, bacterial, unspecified pneumonia
	480.9	Viral pneumonia, unspecified	J12.9	Viral pneumonia, unspecified
	482.9	Bacterial pneumonia, unspecified	J15.9	Unspecified bacterial pneumonia
	485	Bronchopneumonia, organism unspecified	J18.0	Bronchopneumonia, unspecified organism

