	486	Pneumonia, organism unspecified	J18.8 J18.9	Other pneumonia, unspecified organism Pneumonia, unspecified organism

PFIZER CONFIDENTIAL

CT24-WI-GL02-RF02 5.0 Non-Interventional Study Protocol Template For Secondary Data Collection Study 01-Aug-2023

Page 31 of 46

Table 4. Diagnosis Codes for Identifying Invasive Pneumococcal Disease, All-Cause Pneumonia, and Pneumococcal Pneumonia

Condition	ICD-9-CM		ICD-10-CM	
	Codes	Description	Codes	Description
IPD				
Bacteremia	790.7 + 041.2 771.83 + 041.2	Bacteremia + pneumococcus	R78.81 + B95.3	Bacteremia + Streptococcus pneumoniae as the cause of diseases classified elsewhere (Streptococcus pneumoniae)
	038.2	Pneumococcal septicemia	A40.3	Sepsis due to Streptococcus pneumoniae
	038.9 + 041.2	Unspecified septicemia + pneumococcus	A41.9 + B95.3	Sepsis, unspecified organism + Streptococcus pneumoniae
Meningitis	320.1	Pneumococcal meningitis	G00.1	Pneumococcal meningitis
	320.9 + 041.2	Meningitis due to unspecified bacterium + pneumococcus	G00.9 + B95.3 G04.2 + B95.3	Bacterial meningitis, unspecified + Streptococcus pneumoniae Bacterial meningoencephalitis and meningomyelitis, not elsewhere classified + Streptococcus pneumoniae
	322.9 + 041.2	Meningitis, unspecified + pneumococcus	G03.9 + B95.3	Meningitis, unspecified + Streptococcus pneumoniae
Other	421.x + 041.2	Endocarditis + pneumococcus		
	421 + 041.2	Acute and subacute bacterial endocarditis + pneumococcus	I33.0 + B95.3	Acute and subacute infective endocarditis + Streptococcus pneumoniae
	421.1 + 041.2	Acute and subacute infective endocarditis in diseases classified elsewhere + pneumococcus	I39 + B95.3	Endocarditis and heart valve disorders in diseases classified elsewhere + Streptococcus pneumoniae
	421.9 + 041.2	Acute endocarditis, unspecified + pneumococcus	I33.9 + B95.3	Acute and subacute endocarditis, unspecified + Streptococcus pneumoniae
	711.0 + 041.2	Septic arthritis + pneumococcus	M00.00 + B95.3 M00.20 + B95.3 M00.80 + B95.3 M00.9 + B95.3 M00.10 + B95.3	Staphylococcal arthritis, unspecified joint + Streptococcus pneumoniae Other streptococcal arthritis, unspecified joint + Streptococcus pneumoniae Arthritis due to other bacteria, unspecified joint + Streptococcus pneumoniae Pyogenic arthritis, unspecified + Streptococcus pneumoniae Pneumococcal arthritis, unspecified joint + Streptococcus pneumoniae

PFIZER CONFIDENTIAL

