	481	Pneumococcal pneumonia [Streptococcus pneumoniae pneumonia]	J18.1 J13	Lobar pneumonia, unspecified organism Pneumonia due to Streptococcus pneumoniae
	482	Pneumonia due to Klebsiella pneumoniae	J15.0	Pneumonia due to Klebsiella pneumoniae
	482.1	Pneumonia due to Pseudomonas	J15.1	Pneumonia due to Pseudomonas
	482.2	Pneumonia due to Hemophilus influenzae [H. influenzae]	J14	Pneumonia due to Hemophilus influenzae
	482.3	Pneumonia due to Streptococcus , unspecified	J15.4	Pneumonia due to other streptococci
	482.31	Pneumonia due to Streptococcus , group A	J15.4	Pneumonia due to other streptococci
	482.32	Pneumonia due to Streptococcus , group B	J15.3	Pneumonia due to Streptococcus , group B
	482.39	Pneumonia due to other Streptococcus	J15.4	Pneumonia due to other streptococci

PFIZER CONFIDENTIAL

CT24-WI-GL02-RF02 5.0 Non-Interventional Study Protocol Template For Secondary Data Collection Study 01-Aug-2023

Page 38 of 46

	482.4	Pneumonia due to Staphylococcus, unspecified	J15.20	Pneumonia due to staphylococcus, unspecified
	482.41	Methicillin susceptible pneumonia due to Staphylococcus aureus	J15.211	Pneumonia due to Methicillin susceptible Staphylococcus aureus
	482.42	Methicillin resistant pneumonia due to Staphylococcus aureus	J15.212	Pneumonia due to Methicillin resistant Staphylococcus aureus
	482.49	Other Staphylococcus pneumonia	J15.29	Pneumonia due to other staphylococcus
	482.81	Pneumonia due to anaerobes	J15.8	Pneumonia due to other specified bacteria
	482.82	Pneumonia due to escherichia coli [E. coli]	J15.5	Pneumonia due to Escherichia coli
	482.83	Pneumonia due to other gram-negative bacteria	J15.6	Pneumonia due to other aerobic Gram-negative bacteria
	482.84	Pneumonia due to Legionnaires' disease	A48.1	Legionnaires' disease
	482.89	Pneumonia due to other specified bacteria	J15.8	Pneumonia due to other specified bacteria
	482.9	Bacterial pneumonia, unspecified	J15.9	Unspecified bacterial pneumonia
	483	Pneumonia due to mycoplasma pneumoniae	J15.7	Pneumonia due to Mycoplasma pneumoniae
	483.1	Pneumonia due to chlamydia	J16.0	Chlamydial pneumonia
	483.8	Pneumonia due to other specified organism	J16.8	Pneumonia due to other specified infectious organisms
	484.1	Pneumonia in cytomegalic inclusion disease	B25.0	Cytomegaloviral pneumonitis

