	484.3	Pneumonia in whooping cough	A37.91 A37.01 A37.11 A37.81	Whooping cough, unspecified species with pneumonia Whooping cough due to Bordetella pertussis with pneumonia Whooping cough due to Bordetella parapertussis with pneumonia Whooping cough due to other Bordetella species with pneumonia
	484.5	Pneumonia in anthrax	A22.1	Pulmonary anthrax
	484.6	Pneumonia in aspergillosis	B44.0	Invasive pulmonary aspergillosis
	484.7	Pneumonia in other systemic mycoses	J17	Pneumonia in diseases classified elsewhere
	484.8	Pneumonia in other infectious diseases classified elsewhere	J17 B77.81	Pneumonia in diseases classified elsewhere Ascariasis pneumonia
	485	Bronchopneumonia, organism unspecified	J18.0	Bronchopneumonia, unspecified organism

PFIZER CONFIDENTIAL

CT24-WI-GL02-RF02 5.0 Non-Interventional Study Protocol Template For Secondary Data Collection Study 01-Aug-2023

Page 39 of 46

	486	Pneumonia, organism unspecified	J18.8 J18.9	Other pneumonia, unspecified organism Pneumonia, unspecified organism
	487	Influenza with pneumonia	J10.00 J10.08 J11.00 J11.08 J12.9	Influenza due to other identified influenza virus with unspecified type of pneumonia Influenza due to other identified influenza virus with other specified pneumonia Influenza due to unidentified influenza virus with unspecified type of pneumonia Influenza due to unidentified influenza virus with specified pneumonia Viral pneumonia, unspecified
	510.x			Empyema
	510	Empyema with fistula	J86.0	Pyothorax with fistula
	510.9	Empyema without mention of fistula	J86.9	Pyothorax without fistula
			J85.1	Abscess of lung with pneumonia
	136.3	Pneumocystosis	B59	Pneumocystosis
Pneumococca 1	481	Pneumococcal pneumonia	J13	Pneumonia due to Streptococcus pneumoniae
	482.9 + 041.2	Bacterial pneumonia, unspecified + pneumococcus	J15.9 + B95.3	Unspecified bacterial pneumonia + Streptococcus pneumoniae
	485 + 041.2	Bronchopneumonia, organism unspecified + pneumococcus	J18.0 + B95.3	Bronchopneumonia, unspecified organism + Streptococcus pneumoniae
	486 + 041.2	Pneumonia, organism unspecified + pneumococcus	J18.8 + B95.3 J18.9 + B95.3	Other pneumonia, unspecified organism + Streptococcus pneumoniae Pneumonia, unspecified organism + Streptococcus pneumoniae
	510.x + 041.2			Empyema + pneumococcus
	510 + 041.2	Empyema with fistula + pneumococcus	J86.0 + B95.3	Pyothorax with fistula + Streptococcus pneumoniae

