**Table 5.2 Outcomes of Interest**

Outcome Type	Outcome	Definition
Primary outcomes	IPD	ICD-9-CM or ICD-10-CM codes listed in Appendix Table 7.4
	Pneumococcal pneumonia	ICD-9-CM or ICD-10-CM codes listed in Appendix Table 7.4
	All-cause pneumonia	ICD-9-CM or ICD-10-CM codes listed in Appendix Table 7.4
Secondary outcomes	Pneumococcal pneumonia or pneumonia with unspecified causes	ICD-9-CM or ICD-10-CM codes listed in Appendix Table 7.5
	Pneumonia with unspecified causes	ICD-9-CM or ICD-10-CM codes listed in Appendix Table 7.5
Sensitivity analysis outcome	All-cause pneumonia not associated with HIV	ICD-9-CM or ICD-10-CM codes listed in Appendix Table 7.6

For combination diagnosis codes, (e.g., bacteremia + pneumococcus) for diagnoses in an inpatient setting patients must have all codes within the same admission. The latest date of the combination of diagnoses will be used as the diagnosis date. For diagnoses in an outpatient setting patients must have all codes within the same date.

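### J18.1 (lobar pneumonia) is missing from the unspecified-cause list and, with B95.3, from the pneumococcal list; pneumococcal arthritis needs a redundant second code to count as IPD

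*Protocol*

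**What the plan says.** Protocol Section 9.3 (Table 1) and SAP Table 5.2 define each outcome as the codes in an appendix table. Protocol Tables 4 and 5 and SAP Tables 7.4 and 7.5 agree on the following.

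- **All-cause pneumonia.** ICD-9 481 is paired with two ICD-10 codes: J18.1, "Lobar pneumonia, unspecified organism", and J13, "Pneumonia due to Streptococcus pneumoniae".
- **Pneumococcal pneumonia.** ICD-9 481 is paired with J13 only. J18 codes count when B95.3 is present: J18.0 + B95.3, then "J18.8 + B95.3 J18.9 + B95.3".
- **Unspecified causes.** The ICD-10 codes are J12.9, J15.9, J18.0, J18.8 and J18.9. The block opens with an ICD-9 row, 480-486 and 487.0, described as "Viral, bacterial, unspecified pneumonia".
- **IPD.** Every M00.1x code, starting with M00.10, "Pneumococcal arthritis, unspecified joint", is listed only in combination with B95.3. In the same table G00.1, "Pneumococcal meningitis", and A40.3 (pneumococcal sepsis) stand alone.

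For inpatient combinations, SAP Section 5.3.1 states that "patients must have all codes within the same admission". Outpatient combinations need all codes on the same date.

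**The concern.** J18.1 is described as organism-unspecified, yet it is not in the list meant for organism-unspecified pneumonia. When a pneumococcus code accompanies it, it still does not qualify as pneumococcal, unlike its sister codes. No reason is given in either document. A lobar pneumonia claim therefore reaches all-cause pneumonia and no other outcome.

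The arthritis rows have a similar fault. A code that already names the pneumococcus is rejected unless a second code names it again.

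At stake are both secondary outcomes, primary objective 2 (through J18.1 + B95.3) and, slightly, primary objective 1. All-cause pneumonia is unaffected because J18.1 is in its list. No stated precision figure changes either: Protocol Tables 2 and 3 cover only IPD and all-cause pneumonia and rest on assumed incidence rates, not on these code lists.

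**Working it through.** The plan states no figure on this point to reproduce. The check is list membership, plus a count of calendar months.

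**Step 1: J18 codes** (Protocol Tables 4 and 5; SAP Tables 7.4 and 7.5 are the same)

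| Code | All-cause | Unspecified causes | Pneumococcal, with B95.3 |
|---|---|---|---|
| J18.0 | yes | yes | yes |
| J18.1 | yes | **no** | **no** |
| J18.8 | yes | yes | yes |
| J18.9 | yes | yes | yes |

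J18.1 is the only one of the four missing from either list. It follows that:

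- J18.1 without B95.3 is lost to both secondary outcomes.
- J18.1 with B95.3 is lost to primary objective 2 and to both secondary outcomes.
- An event is lost only if no other qualifying code is recorded in the episode.

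**Step 2: arthritis codes.** The M00.1x codes are M00.10, seven joint sites with three laterality codes each, M00.18 and M00.19: 1 + 7 × 3 + 2 = 24. All 24 carry the B95.3 requirement. Organism-specific codes accepted alone are 038.2/A40.3 and 320.1/G00.1 for IPD, and 481/J13 for pneumococcal pneumonia. On the ICD-9 side the arthritis codes (711.0x) do not name an organism, so a second code is needed there. M00.1x does name it.

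**Step 3: the ICD-9 range row.** Table 4 lists 36 ICD-9 rows within 480-486 and 487: six in 480, one in 481, seventeen in 482, three in 483, six in 484, and one each in 485, 486 and 487. The unspecified-cause block itemises four (480.9, 482.9, 485, 486). If the range row were applied as a code rule, 36 − 4 = 32 further rows would enter for ICD-9 claims, including pneumococcal 481.

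**Step 4: share of follow-up under ICD-9.** Data start in January 2014, and follow-up begins after a six-month baseline (Protocol Section 9.1), so no earlier than about July 2014. The study ends in September 2022.

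- Possible follow-up months: 6 (2014) + 7 × 12 (2015 to 2021) + 9 (2022) = 99.
- ICD-9 months if ICD-9 applies through September 2015 (an assumption; the documents give no date): 6 + 9 = 15.
- Share: 15/99 = 15%. ICD-10 share: 84/99 = 85%.
- If the switch fell three months earlier or later: 12/99 = 12% or 18/99 = 18%.

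These are calendar months, not person-time or events. Index dates are staggered, so person-time need not follow the same split.

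**The case against.** The strongest reply is that this is a clerical matter with no demonstrated bias. The same lists apply to vaccinated and unvaccinated time, the documents give no frequency for J18.1 or M00.1x, and leaving an organism-unspecified code out of a pneumococcal outcome follows its label. Much of this stands: no direction or size of error in VE can be shown. The last argument does not cover J18.1 + B95.3, because J18.0, J18.8 and J18.9 are also organism-unspecified and count with B95.3. Nor does it explain the omission from the unspecified-cause list.

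A reader might infer several stronger points that the documents do not support.

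- **That the unspecified outcome is nearly all pneumonia for ICD-9 claims.** The range row is most likely a heading. It has no ICD-10 counterpart and is followed by itemised codes, like the 421.x, 730.0x and 510.x rows. Protocol Table 11 keeps the same row while dropping 484.1, 484.6 and 484.7, which a literal reading would restore. Still, no text calls it a heading.
- **That pneumococcal pneumonia changes meaning between coding systems because 481 also captures unspecified lobar pneumonia.** The 481 to J18.1 pairing occurs only in the all-cause rows, where both codes count. Everywhere else 481 is described as pneumococcal.
- **That codes printed without a trailing .0 will be mismatched.** An example is 487, "Influenza with pneumonia", against 487.0 in the range row. The descriptions identify the intended codes, and neither exact nor prefix matching is specified, so this is a display matter.
- **That staphylococcal arthritis with B95.3 must be removed.** B95.3 still documents the pneumococcus, so this is a choice about specificity.
- **That 20% of the study is ICD-9.** Counting 21 of 105 calendar months ignores the baseline period, during which outcomes do not count.

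**Conclusion.** The point holds as a specific, low-priority correction to the code lists. As written, they drop ICD-10 lobar pneumonia from both secondary outcomes, drop J18.1 + B95.3 from primary objective 2, and drop M00.1x without B95.3 from IPD. The size is unknown because the documents contain no code frequencies; the IPD part is probably small. The gap concerns ICD-10 claims, about 85% of possible follow-up months if ICD-9 ends in September 2015. The likely consequence is fewer captured events, and so lower incidence rates and wider intervals for these outcomes. A bias in VE, or a false waning pattern from the coding change, is not shown. The range row calls for clarification and is not a demonstrated misclassification.

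**What to change.** - In Protocol Table 5 and SAP Table 7.5, add J18.1 to the unspecified-cause list.
- In Protocol Tables 4 and 5 and SAP Tables 7.4 and 7.5, add J18.1 + B95.3 to the pneumococcal list.
- In Protocol Table 4 and SAP Table 7.4, let M00.1x count as IPD without B95.3.
- In Protocol Table 5 and SAP Table 7.5, delete the 480-486/487.0 row under unspecified causes or mark it as a heading, so that it cannot bring 481 and other organism-specific codes into that outcome.

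The edit is small, but it comes after outcome extraction began. The SAP amendment log shows that recurrent events had already been generated by June 2023, when the episode gap was lengthened. The affected outcomes must be re-run. The change should be recorded as a dated amendment stating which results had been seen by then, since Protocol Section 9.7 requires a protocol amendment for major changes to primary endpoint definitions. Reporting event counts under the old and new lists would show how much the change matters. The planned final report date is 30 October 2024.

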		
Adherence will be measured as 'Proportion of days covered = (Number of days covered by any ART, excluding ritonavir and cobicistat) ÷ (total days)*100'[27] every six months
 
Individuals with >80% of days covered will be classified as 'adherent' and individuals with ≤80% of days covered will be classified as 'non-adherent'[27]
	
	CD4 cell count	Categorized as <200, 200-499, ≥500 cells/mm ³	Baseline and follow-up
	PPSV23 vaccination	NDC and CPT codes listed in Appendix Table 8	Baseline and follow-up
	Annual CD4 laboratory test	
CD4 laboratory tests will be identified by CPT codes listed in Appendix Table 9
 
Individuals who have at least one CD4 laboratory test performed during each year of follow-up
	Baseline and follow-up
	Annual viral load laboratory test	
Viral load laboratory tests will be identified by CPT codes listed in Appendix Table 10
 
Individuals who have at least one viral load laboratory test performed during each year of follow-up
	Baseline and follow-up
	Respiratory virus season	Respiratory virus season occurs between October 1 and April 30	Follow-up
Sensitivity analysis outcome	All-cause pneumonia not associated with HIV	ICD-9-CM or ICD-10-CM codes listed in Appendix Table 11	Follow-up

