Several stratified analyses will be conducted. PPSV23 is recommended for PLWH and feasibility data provided by Komodo suggest that one in four PWLH who received PCV13 during 2014-2015 also received PPSV23 within two years. Rather than censor or exclude

individuals who receive PPSV23, we will calculate PCV13 VE among PWLH who have/have not received PPSV23 before and during the study period.

Feasibility assessments from Komodo indicate that approximately 25% of PWLH have at least one CD4 cell count or percentage laboratory result available. Therefore, we will calculate PCV13 VE among the subset of PWLH who have a CD4 cell count during the baseline period or follow-up, and potentially stratify by CD4 category using each patient's lowest value during the study.

Additional VE stratifications by ART adherence during follow-up, year of HIV diagnosis, and age will be assessed for feasibility as well, as these affect patients' immune status and immune reconstitution. Due to possible waning of the VE and different lengths of follow-up by index year, VE stratification by year of HIV diagnosis will be restricted to the first 3 years of follow-up.

A sensitivity analysis will also be conducted. In this analysis, causes of pneumonia that are characteristic of HIV, for example pneumonia due to cytomegalovirus, mycobacteria, and fungi, will be excluded from our definition of all-cause pneumonia.

Residual confounding of our VE estimates due to inadequate control for health care seeking behavior and immune status in our analyses will be explored. To do so, we will employ a negative control exposure and a negative control outcome. Potential negative control exposures include vaccinations that are recommended for PLWH but would not be expected to have any protective effect against the pneumonia outcomes of interest. If residual confounding does not exist, the negative control vaccine would not have an effect on the pneumonia outcomes. However, if the analysis demonstrates that the negative control vaccine protects against these outcomes, this suggests the presence of residual confounding.

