9.9. Limitations of the Research Methods

There are several limitations in this study. Given that this is an observational study using health care administrative claims data, residual confounding due to missing or unmeasured information is possible. To examine this, we will assess the effect of PCV13 on a negative control outcome and the effect of a negative control exposure on our outcomes of interest. If the HRs in any of these models are less than 1.0, it would indicate that residual confounding exists and may result in adjustment of our VE estimates.

Second, health care administrative claims data will be available from January 1, 2014 through September 30, 2022. The recommendation to vaccinate all PLWH was published in June 2012, and some PLWH may have received PCV13 prior to January 1, 2014 and be misclassified as unvaccinated. In addition, PLWH eligible for the study may have received PCV13 vaccination during a time period in which we do not have their claims data. Misclassification of PCV13 vaccine status may lead to lower estimates of vaccine effectiveness than in truth, because our unvaccinated cohort will incorrectly include vaccinated PLWH.

In addition, we are using ICD-9-CM and ICD-10-CM codes to define HIV infection. Our definition of HIV infection requires at least one HIV-related diagnosis code in the inpatient setting or at least two HIV-related diagnosis codes in the outpatient setting. While this definition of HIV has been used in previous administrative claims database studies, it is possible that these codes may be used by health care providers to order laboratory tests to rule out HIV infection and thus, some individuals without HIV will be included in our study population.

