	510.9 + 041.2	Empyema without mention of fistula + pneumococcus	J86.9 + B95.3	Pyothorax without fistula + Streptococcus pneumoniae

PFIZER CONFIDENTIAL

CT24-WI-GL02-RF02 5.0 Non-Interventional Study Protocol Template For Secondary Data Collection Study 01-Aug-2023

Page 40 of 46

Table 6. National Drug Codes and Procedure Codes for Identifying Immunosuppressive Medications (see excel)

Table 7. National Drug Codes and Procedure Codes for Identifying Influenza Vaccinations (see excel)

Table 8. National Drug Codes and CPT® Codes for Identifying PPSV23 Vaccination

Code	Type	Description
90732	CPT	Pneumovax 23
00006473900	NDC	Pneumovax 23
00006473901	NDC	Pneumovax 23
00006473950	NDC	Pneumovax 23
00006474100	NDC	Pneumovax 23
00006483701	NDC	Pneumovax 23
00006483702	NDC	Pneumovax 23
00006483703	NDC	Pneumovax 23
00006489400	NDC	Pneumovax 23
00006489400	NDC	Pneumovax 23
00006494300	NDC	Pneumovax 23
00006494301	NDC	Pneumovax 23
00247040201	NDC	Pneumovax 23
50090145200	NDC	Pneumovax 23
50090145209	NDC	Pneumovax 23
54569141200	NDC	Pneumovax 23
54569653800	NDC	Pneumovax 23
54868333901	NDC	Pneumovax 23
54868333909	NDC	Pneumovax 23
54868432000	NDC	Pneumovax 23
54868432009	NDC	Pneumovax 23
55045354202	NDC	Pneumovax 23
00005230931	NDC	Pnu-Imune 23
00005230933	NDC	Pnu-Imune 23
54868070700	NDC	Pnu-Imune 23

Table 9. CPT® codes to identify CD4 laboratory tests

Code	Type	Description
86361	CPT	Absolute CD4 count
86360	CPT	Absolute CD4 and CD8 counts with ratio

Table 10. CPT® codes to identify viral load laboratory tests

Code	Type	Description
87534	CPT	Infectious agent detection by nucleic acid (DNA or RNA); HIV-1, direct probe technique
87535	CPT	Infectious agent detection by nucleic acid (DNA or RNA); HIV-1, amplified probe technique
87536	CPT	Infectious agent detection by nucleic acid (DNA or RNA); HIV-1, quantification

Table 11. Diagnosis Codes for Identifying All-Cause Pneumonia not due to HIV

Condition	ICD-9-CM		ICD-10-CM		
	Codes	Description	Codes	Description	
		Viral, bacterial, unspecified pneumonia			
All-Cause	480-486 487.0				
	480	Pneumonia due to adenovirus	J12.0	Adenoviral pneumonia	
	480.1	Pneumonia due to respiratory syncytial virus	J12.1	Respiratory syncytial virus pneumonia	
	480.2	Pneumonia due to parainfluenza virus	J12.2	Parainfluenza virus pneumonia	
	480.3	Pneumonia due to SARS-associated coronavirus	J12.81 J12.82	Pneumonia due to SARS-associated coronavirus Pneumonia due to coronavirus disease 2019	

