Any hospitalization	Evidence of inpatient claim(s) Yes, No	Descriptive, covariate	Baseline and follow-up
Hodgkin's lymphoma	ICD-9-CM or ICD-10-CM codes listed in Protocol Annex 1.11 Yes, No	Descriptive, covariate	Baseline and follow-up
Opportunistic infections	ICD-9-CM or ICD-10-CM codes listed in Protocol Annex Table 14	Descriptive, covariate	Baseline and follow-up

	Yes, No  Note: In the analysis of all-cause pneumonia, pneumocystis jirovecii pneumonia codes are excluded from the follow-up. In the analysis of candidiasis negative control outcomes, candidiasis infection codes are excluded from the follow-up.		
Antiretroviral treatment (ART) adherence	ART use will be identified by NDC codes listed in Appendix Table 7.2  Adherence will be measured as 'Proportion of days covered = (Number of days covered by any ART, excluding ritonavir and cobicistat) ÷ (total days)*100'[8] every six months  Individuals with >80% of days covered will be classified as 'adherent' and individuals with ≤80% of days covered will be classified as 'non-adherent'[8]. Individuals without ART information will be classified as Missing. As a subgroup, ART adherence will be calculated using the information over the entire follow-up.	Descriptive, covariate, subgroup	Baseline and follow-up
CD4 cell count	Categorized as <200, 200-499, ≥500 cells/mm 	Descriptive, subgroup	Baseline and follow-up
PPSV23 vaccination	NDC and CPT codes listed in Appendix Table 7.9  Yes, No. 0, 1, 2+ doses	Descriptive, subgroup	Before first HIV diagnosis, baseline and follow-up
Annual CD4 laboratory test	CD4 laboratory tests will be identified by CPT codes listed in Appendix Table 7.11  Individuals who have at least one CD4 laboratory test performed during each year of follow-up Yes, No	Covariate	Baseline and follow-up
Annual viral load laboratory test	Viral load laboratory tests will be identified by CPT codes listed in Appendix Table 7.12  Individuals who have at least one viral load laboratory test performed during each year of follow-up Yes, No	Covariate	Baseline and follow-up

Respiratory virus season	Respiratory virus season occurs between October 1 and April 30 Yes, No	Covariate	Follow-up
--------------------------	---	-----------	-----------

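### The annual CD4-test covariate in the weights is read from two claim codes only, although the study holds dated CD4 results that could show a test was done; two viral-load codes also merit a sensitivity analysis.

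*Protocol*

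**What the plan says.** **CD4 test.** Protocol Section 9.3, Table 1, states: "CD4 laboratory tests will be identified by CPT codes listed in Appendix Table 9". SAP Table 5.3 repeats the rule, pointing to its own Table 7.11. Both lists hold two codes: 86361 (absolute CD4 count) and 86360 (absolute CD4 and CD8 counts with ratio).

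**Viral-load test.** Protocol Table 1 states: "Viral load laboratory tests will be identified by CPT codes listed in Appendix Table 10". The three codes, repeated in SAP Table 7.12, are described as follows:
- 87534: "Infectious agent detection by nucleic acid (DNA or RNA); HIV-1, direct probe technique"
- 87535: "Infectious agent detection by nucleic acid (DNA or RNA); HIV-1, amplified probe technique"
- 87536: "Infectious agent detection by nucleic acid (DNA or RNA); HIV-1, quantification"

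**Timing and missing records.** SAP Section 5.3.2 codes each flag Yes for up to 365 days after the last test. Protocol Section 9.8 takes the absence of a record to mean the absence of the event.

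**Purpose and use.** Protocol Section 5 (version 2.0) says both flags were added to reduce confounding by differences in HIV care seeking. They are time-varying, so under SAP Section 5.8.4 they enter the denominators of the treatment weights and, by the same method, of the censoring weights.

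**Laboratory data.** Protocol Section 9.2 says the vendor supplies HIV-related laboratory data. Section 9.7 says "approximately 25% of PWLH have at least one CD4 cell count or percentage laboratory result available" and plans a VE analysis in people who have a CD4 count. SAP Table 5.3 gives CD4 cell count a descriptive and subgroup role, not a covariate role.

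**The concern.** A dated CD4 result is direct evidence that a CD4 test was done. The plan relies on such results to define a subset but does not count them in the flag whose purpose is to record testing. Someone with a CD4 count on file and no 86360 or 86361 claim is treated as untested. SAP Section 5.8.4 regenerates the weights within each subgroup, so this can happen inside the CD4-result analysis itself.

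CD4 values will be missing for most people (Protocol Section 9.7), which leaves the two test flags among the limited set of HIV-care proxies in the weights. If they are measured with error, some care-seeking confounding may stay in the weighted VE.

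The viral-load list raises a smaller question. A load is a quantity, and two of the three codes are not described as measuring one. Neither document explains their inclusion.

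**Working it through.** The plan states no figure for this point, so there is none to reproduce. The check has two parts.

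**1. The text side by side**

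| Item | Source used | Where |
|---|---|---|
| Annual CD4-test flag | Claims 86360, 86361 | Protocol Table 1 and Appendix Table 9; SAP Tables 5.3 and 7.11 |
| CD4-result subset and strata | Laboratory results | Protocol 9.7; SAP 5.2.3 and Table 5.3 |
| No record found | Coded as absent | Protocol 9.8 |

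A certain false No arises when a dated CD4 result exists and no listed claim falls in the preceding 365 days. If the 25% applies to the 175,000 people in Protocol Section 9.5, at most 0.25 × 175,000 = 43,750 people could be affected. That is everyone with any result at any time. The number with a result and no claim is not given, nor is the number whose only viral-load evidence is 87534 or 87535.

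**2. Illustration of size**

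Every input except the roughly 32% overall uptake (56,000/175,000) is an assumption. True VE is 0 and 65% of people are engaged in care. The pneumonia rate is 1 in the unengaged.

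- Stronger case: uptake 42% engaged and 14% unengaged; rate ratio for engagement 0.6. Overall uptake is 0.65 × 0.42 + 0.35 × 0.14 = 0.322.
- Weaker case: 40% and 18%; rate ratio 0.7. Overall uptake is 0.323.

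The viral-load flag is wrongly Yes for 10% of the unengaged. The CD4 flag is wrongly No for 10% of the engaged. The errors are independent and both flags are adjusted for, as planned. The strata are:

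- both Yes: 0.65 × 0.9 = 0.585, all engaged
- viral load Yes, CD4 No: 0.065 engaged + 0.035 unengaged = 0.100
- both No: 0.35 × 0.9 = 0.315, all unengaged

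Residual false VE = 1 − Σ(stratum share × vaccinated rate) / Σ(stratum share × unvaccinated rate). Only the mixed stratum is confounded.

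*Stronger case, mixed stratum*
- Vaccinated: (0.065 × 0.42 × 0.6 + 0.035 × 0.14) / (0.065 × 0.42 + 0.035 × 0.14) = 0.02128/0.0322 = 0.6609
- Unvaccinated: (0.065 × 0.58 × 0.6 + 0.035 × 0.86) / (0.065 × 0.58 + 0.035 × 0.86) = 0.05272/0.0678 = 0.7776
- Totals: 0.351 + 0.0661 + 0.315 = 0.7321 and 0.351 + 0.0778 + 0.315 = 0.7438
- False VE: 1 − 0.7321/0.7438 = **1.6 points**

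*Weaker case, mixed stratum*
- Rates: 0.0245/0.0323 = 0.7585 and 0.0560/0.0677 = 0.8272
- Totals: 0.4095 + 0.0759 + 0.315 = 0.8004 and 0.4095 + 0.0827 + 0.315 = 0.8072
- False VE: **0.9 points**

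The mixed stratum has the cohort's own 65/35 make-up, so it carries the full crude confounding (1 − 0.6609/0.7776 = 15.0% in the stronger case), but it holds only a tenth of the people. If one flag is correct, no stratum is mixed and the residual is 0.

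For scale, Protocol Section 9.5 assumes an all-cause pneumonia VE of 5% to 15%, and the intervals in its Table 3 have half-widths of about 2 to 4 points, from (17 − 13)/2 to (9 − 1)/2.

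**The case against.** The best defence is that the flags stand for care seeking, not for a test result. A paid claim is a reasonable record that a test was done. A nucleic-acid HIV test in someone who meets the HIV definition can still reflect contact with care. ART adherence, influenza vaccination, physical examinations and hospitalization are also in the weights. Negative controls are planned for residual confounding, with a possible bias correction. Adding results available for about a quarter of people also makes the flag depend on laboratory coverage.

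Most of this stands, and it limits the weight of the point. It gives no reason to code No when a dated result shows that a test took place.

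A reader might infer more than the documents support:

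- *That CD4 results are ignored, or that every weight is wrong.* Results are used descriptively and for a subset. The flags enter every denominator model, but a given value is wrong only in the circumstances above, and the treatment-weight contributions after vaccination are set to 1.
- *That people being ruled out for HIV are counted as monitored.* Protocol Section 9.9 says "it is possible that these codes may be used by health care providers to order laboratory tests to rule out HIV infection", but the codes meant there are ICD diagnosis codes, and no test is named. Nor does any descriptor call 87534 or 87535 qualitative; all three begin with detection.
- *That VE is overstated.* If the false Yes values fell on people without HIV, who may be at low risk and seldom vaccinated, the bias could run the other way. Protocol Section 7 puts IPD incidence in people with HIV at about 30 times that of the general population.
- *That as much as 7 points remain.* Putting both 10% errors on a single flag gives 7.3 points in the stronger case and 3.7 in the weaker. The false Yes belongs to the viral-load flag and the false No to the CD4 flag, and the plan adjusts for both.

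**Conclusion.** The CD4 point holds as a gap in the covariate definition and is worth closing because it is cheap. The flag omits evidence the study already holds, and the same person can be in the CD4-result subset and weighted as untested.

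The viral-load point is weaker. For a care-seeking proxy, removing 87534 and 87535 from the main covariate is a trade-off: some in-care people would lose a true Yes. It belongs in a sensitivity analysis.

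No bias in VE has been shown. Its size and direction cannot be found from the documents, which give no error rates. About 1 to 2 points is an illustration that assumes 10% error in each flag, independent errors, engaged people vaccinated more and at lower risk, and no help from other covariates. Help from other covariates or lower error rates would reduce it. Errors falling on the same people in both flags would raise it; the documents do not indicate whether that happens.

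**What to change.** 1. In Protocol Section 9.3, Table 1, and in SAP Section 5.3.2 and Table 5.3, code the annual CD4 test Yes on either a listed CPT claim or a dated CD4 result (count or percentage) in the laboratory data, with the same 365-day rule. Do likewise for viral load if such results are supplied; the documents confirm CD4 results but do not mention viral-load results.
2. Tabulate, by vaccination status, how many person-intervals change from No to Yes. This supplies the missing error rate for the CD4 flag.
3. Keep the claims-only flags as a sensitivity analysis, because the new definition depends partly on laboratory-data coverage.
4. Run the weights with 87536 alone as a second sensitivity analysis, and state why 87534 and 87535 are in the main list.

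The cost is a text edit, one merge with data the study already receives, and re-running the weights for the two sensitivity analyses. Nothing else in the design changes.
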